6.3. Pregnancy and breastfeeding

For female subjects with childbearing potential (they have had at least one period during the last 12 months), a urine pregnancy test will be performed at the inclusion visit, to ensure the subject is not pregnant. The urine pregnancy test will be performed by dipstick at the trial site. Furthermore, the female subjects should not be breastfeeding, when participating in the clinical investigation.

6.4. Recruitment and enrolment

Recruitment of potential subjects will begin once approval have been obtained from the Ethics Committee (EC).

Recruitment will occur through competitive enrolment at 3 different sites in Denmark. The recruitment period from first subject enrolled to last subject enrolled will be approximately 4 months.

Recruitment from hospitals will be via patient screening visits or subject records kept at the participating sites. The Coloplast Clinical Manager will have close contact to each site during the recruitment and enrolment period.

Sites will be instructed to enrol 22-24 eligible hospitalized subjects at a competitive rate. Once the Coloplast Clinical Manager is aware, that 67 subjects have been enrolled, the recruitment will stop.

If, at this time, there are subjects, who have been informed about the investigation (V0) and are reflecting on participation, they will be given the opportunity to be included within the 24 hours post V0.

Recruitment method	Hospital
Potential subjects	Recruitment will go through the Hospital sites. Potential subjects are identified by screening in patient journals using the following searching criteria: 
 • ≥ 18 years of age • Hospital-admitted patients with a limited level of mobility and a Braden score between 6-18 • Expected hospital stay of at least 72 hours
First contact	The potential subjects will be contacted during a planned visit in the ward at the hospital. If a subject is eligible and interested in participating in the investigation upon a short introduction, then written information about the investigation (Informed Consent Form) will be distributed to the subject. The Principal Investigator or delegate will invite the subject to a Screening Visit (V0).
Screening Visit (V0)	At the scheduled Screening Visit (V0) the Principal Investigator or delegate will introduce the investigation and review the inclusion and exclusion criteria. If the subject wishes to reconsider his/her participation at V0, the subject has the right to wait minimum 24 hours before deciding on participation. If the subject hereafter decides to participate in the clinical investigation a Baseline Visit (V1) will be scheduled unless performed the same day as the Screening Visit. If the subject does not meet the inclusion criteria or meet the exclusion criteria, this will be registered at the Subject Pre-Screening Log.
Baseline Visit (V1)	If the subject decides to participate and it is certain, that it is understood, what the investigation entails, the subject will be asked to sign the ICF. When the ICF is signed the subject is considered included in the investigation.

Table 4: Overview of the recruitment process

6.5. Subject withdrawal criteria

The subject can withdraw from the investigation at any time for whatever reason, without any consequences for their future treatment outside the clinical investigation. The Investigator may withdraw a subject from the investigation at any time if they judge it to be the subject's interest.

If dropouts are more than 17 subjects, which entails less than 50 completers, subjects shall be replaced by new subjects.

The investigator must withdraw a subject from the investigation due to:

- Noncompliance with the CIP impacting the scientific integrity of the investigation.
- If subject's safety and wellbeing is compromised by further participation.

- Subjects lost to follow-up. At least three documented attempts will be made to verify subjects lost to follow-up.

Subjects who are prescribed steroid creme for the sacral area, while participating in the investigation, must be withdrawn.

Withdrawn subjects will not be replaced by new subjects. A subject who is withdrawn from the investigation, for any reason, will be encouraged to contact the investigator if problem arises, that the subject believes are related to the clinical investigation. Subject who has not experienced any adverse events, will not be followed up. For subjects who experience adverse events see section 18.1.

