7.1. Clinical investigation-related procedures

Screening Visit (V0), Day 0:

- Introduction to the investigation and review of Subject information Form
- Check of in- and exclusion criteria
- Informed Consent Form – ICF signed at Visit 0. If subject wishes to have time for consideration, it is possible and the ICF is signed at Visit 1 the following day
- Inclusion in investigation and allocation of subject number after ICF is signed

Baseline Visit (V1), Day 1:

- Introduction to the investigation and review of Subject information Form
- ICF signed (if not signed at Visit 0)
- Confirmation of inclusion and exclusion criteria if more than 24 hours has passed since Visit 0
- Collect baseline information:
 - Gender (male/female)
 - Age (at time of enrollment (years)
 - Height (cm)
 - Weight (kg)
 - Urinary incontinence (Y/N)
 - Faecal incontinence (Y/N)
 - Date and main reason for admission (e.g., diabetes mellitus, cardiovascular disease, renal disease, pulmonary disease, anaemia, trauma, other)
 - Skin inspection
 - Braden Scale Score
- Apply Biatain Silicone Bandage on the sacral area

Baseline 2-7, skin inspection, Day 2-7:

- Partial lift of test product and skin inspection for signs of non-blanchable erythema over bony prominence/sacral pressure injury over bony prominence

- Re-application of the test product
- Has there been a test product change (Y/N)?
 - if yes, please register what the cause of the change was (dressing soilage, weakened border, damp/saturated dressing, bulky foam, other)

Termination Visit 8, Day 8 or at the day of discharge/earlier termination date:

- Have signs of non-blanchable erythema over bony prominence/sacral pressure injury over bony prominence developed (Y/N)?
 - If yes, please specify stage of pressure injury (*Appendix 3*)
- Was there any non-compliance to the local pressure injury prevention guideline (Y/N)?
 - If yes, explain non-compliance
 - if yes, please include a summary in the comment page

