18.2. Adverse device effect

An adverse event, which is related to the use of the investigational medical device, is an adverse device effect, and should be marked as unlikely related, possible related, probable related or with causal relationship on the adverse event form.

The definition of an adverse device effect includes any event resulting from insufficiencies or inadequacies in the instruction for use, deployment, implantation, installation and operation, or any malfunction of the medical device, as well as any event resulting from use error or from intentional misuse of the device.

Table 6 lists anticipated adverse device effects that may occur, based on the IFU and their likely incidence rates based on adverse events reported in clinical studies⁴.

Table 6

ANTICIPATED ADE	INCIDENCE RATES
Local pressure injury/Erythema*	1-10%
Skin irritation/inflammation/itching	0.1 %-1%
Maceration and/or local fungus infection of the skin	0.01-0.1%
Pain	0.01-0.1%
Blistering	0.01-0.1%
Allergic skin reaction	Not known

* *Temporary redness/erythema upon removal of the sacral bandage is not considered an adverse device effect, however an abnormal development in intensity or duration should be considered as such.*

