18.5. Medical care of subjects

Principal Investigator shall ensure that adequate medical care is provided, during and after participation in the clinical investigation, to a subject experiencing an adverse event. All ongoing ADEs, SAEs, SADEs and DDs, that could have led to a SAE at subject termination, will be followed according to the Risk Benefit analysis (see 8.2) An ongoing adverse event at subject termination visit is documented as the current status for the adverse event and will not be followed up.

The subjects shall be informed of any new significant findings occurring during the clinical investigation, including the need for additional medical care that can be required, and of the nature and possible cause of any adverse events experienced

Principal Investigator shall provide the subject with the necessary instructions on proper use, handling storage and return of the investigational device and comparator, when it is used or operated by the subject.

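### Withdrawal under 6.5 also stops the scheduled skin inspections and adverse event reviews, so later events in subjects whose skin may have reacted are not actively sought

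*Combined protocol and SAP*

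**What the plan says.** - **Triggers (6.5).** "Subjects who are prescribed steroid creme for the sacral area, while participating in the investigation, must be withdrawn". Withdrawal is also mandatory "If subject's safety and wellbeing is compromised by further participation". Both rules remove the subject from the investigation. No rule covers a subject who stops the dressing but stays in.
- **Timing (7.1, Table 5).** The last visit is "Termination Visit 8, Day 8 or at the day of discharge/earlier termination date". Sacral skin inspection and adverse event review are listed at Visits 2–7 and at termination, and nothing comes after that.
- **After withdrawal (6.5).** Subjects are encouraged to make contact about problems they think are related to the investigation. "Subject who has not experienced any adverse events, will not be followed up". "For subjects who experience adverse events see section 18.1", but 18.1 only defines an adverse event and its intensity grades.
- **Events ongoing at termination (18.5).** "All ongoing ADEs, SAEs, SADEs and DDs, that could have led to a SAE at subject termination, will be followed", with a reference to 8.2, which is a risk-benefit discussion without any schedule or duration. For the rest: "An ongoing adverse event at subject termination visit is documented as the current status for the adverse event and will not be followed up".
- **Known device risks.** Section 8.2 names skin irritation and mechanical trauma. Table 6 lists "Skin irritation/inflammation/itching" at 0.1–1% and gives the rate of allergic skin reaction as not known.
- **Endpoints.** The primary endpoint is the number of adverse events (5.2). The exploratory endpoint is a new sacral pressure injury over the investigation period, yes or no (5.4). The matching objective in 3.1 is limited to injuries that arise with the dressing on.

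**The concern.** Stopping a product and ending observation are separate decisions, and 6.5 makes them one. A subject withdrawn on Day 3 may still be on the ward, at the same risk of a sacral injury, with no further scheduled check of the sacrum. From then on, detection depends on the subject noticing a problem and attributing it to the study. The primary endpoint counts events whether or not they are related. The eligible Braden range of 6–18 also takes in patients with limited sensation, who may not notice a sacral lesion.

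The loss may not be random. The wellbeing trigger refers to harm from taking part. The steroid trigger could, in some subjects, follow a skin reaction of a kind that the plan itself anticipates. If so, observation stops more often in subjects whose skin is in trouble. Missing later events would then make both the adverse event count and the pressure-injury proportion look better than they are.

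**Working it through.** **1. Scheduled observation removed.** Visits after application are V2 to V8, which is 7. Termination at V2 loses 6 of them; termination at V3 loses 5 (V4–V8). These are maxima, because they assume that the subject would otherwise have stayed to Day 8.

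**2. What happens to each kind of event.**

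| Event | Governing text | Result |
|---|---|---|
| The event that led to withdrawal | Skin check and event review at termination (7.1, Table 5); device effects to the sponsor within 24 hours (18.7); safety population is everyone with valid consent (10.1) | Counted |
| Device effect or serious event ongoing at termination | 18.5, pointing to 8.2 | Followed, but no schedule or duration |
| Any other adverse event ongoing at termination | 18.5 | Closed at current status |
| New event or sacral injury after termination | 6.5 | Known only if the subject makes contact |

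The gap is the last two rows.

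**3. Direction of the error.** For the event count, unrecorded events can only lower it. For the pressure-injury proportion there are two cases, because 10.1 assigns the endpoint to the ITT population and then computes it in completed subjects, while section 6 counts 24 hours of wear as completion.
- If a subject withdrawn on Day 3 without injury is kept as a No, a later injury is missed and the proportion is too low.
- If that subject is dropped, the proportion is too low when withdrawn subjects have a higher injury risk than those who stay.

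**4. Number affected.** Using the Table 6 irritation rate and 67 enrolled:
- Expected subjects: 67 × 0.001 = 0.067 to 67 × 0.01 = 0.67.
- Chance of at least one: 1 − 0.999^67 = 6% to 1 − 0.99^67 = 49%.

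No rate is given for allergic reactions, for wellbeing withdrawals, or for how often irritation leads to steroid cream.

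**5. Weight of one injury.** Section 10.2 aims for an exact upper 95% limit of 7.2% or less with 50 completers, at a true rate of 1.2%, with power above 80%. With the two-sided exact interval:
- 0/50: upper limit = 1 − 0.025^(1/50) = 7.11%, so the target is met.
- 1/50: upper limit solves (1 − p)^50 + 50p(1 − p)^49 = 0.025, which gives 10.65%, so the target is missed.

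Only zero injuries meets the target. The probability of that is 0.988^50 = 54.7%, so the stated power is not reproduced. That is a separate matter, and this point does not rest on it. The expected number of injuries is 50 × 0.012 = 0.6, so one injury more or less decides the result. If all 67 subjects were observed, 1/67 would give an upper limit of 8.0%, which also misses 7.2%. At 1/50 the limit also exceeds 10.1%, the upper limit for the comparator control group in 10.4; at 1/67 it does not.

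**The case against.** The case on the other side is substantial, and it limits how far the point can go.

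- **A reader might infer that withdrawal ends all safety observation.** It does not. A device-related irritation still present at termination is an ongoing device effect, and 18.5 says that it will be followed. The sentence denying follow-up in 6.5 applies only to subjects with no adverse event.
- **A reader might infer that the subjects most harmed drop out of the primary endpoint.** They do not. Their triggering event is reported, checked at the termination visit, covered by full monitoring of event records (9.1.3) and counted in a safety population that keeps them.
- **A reader might infer that steroid cream is usually a response to the dressing.** No text says so. The reason given in 6.2 is that steroid may affect the skin, and inpatients can need the cream for other causes. The link is plausible, not established.
- **A reader might take the 30% drop-out allowance as the size of the problem.** That figure covers drop-out from any cause. Table 6 is the nearer guide, and it points to fewer than one subject by the irritation route.
- **The objective in 3.1 concerns injuries during wear,** so an injury after the dressing is stopped arguably falls outside it. Discharge also ends observation by design, and the endpoint is exploratory.

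The first four objections stand in full. The fifth stands in part: 5.4 defines the endpoint over the investigation period, so the two sections leave open whether an injury after stopping counts. None of them covers new events after withdrawal, or ongoing events outside the list in 18.5.

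**Conclusion.** The point holds in a limited form. Withdrawal under 6.5 ends the scheduled skin inspections and adverse event reviews, leaves new events to self-report and closes some ongoing events unresolved. Because the triggers can relate to skin harm, the loss may be informative, and in that case it favours the device. The number of subjects is probably small (0.07–0.67 of 67 by the irritation route), but a single missed sacral injury moves the exact upper limit from 7.1% to 10.65% in 50 completers.

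This rests on three assumptions: that Table 6 rates apply to this population, that some triggers reflect skin reactions, and that the qualifying clause about potential serious events in 18.5 applies to device deficiencies only. If that clause limited device effects as well, the gap would be wider. The documents do not support the stronger conclusion that the safety result is invalid or that harmed subjects go uncounted. This is a cheap improvement, not a flaw that undermines the study.

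**What to change.** Leave the clinical decisions on dressing, cream and withdrawal as the sponsor sets them, and change what happens to observation.

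1. In 6.5, 7.1 and Table 5, state that a subject taken off the dressing who still consents and is still on the ward continues the scheduled sacral skin inspection and adverse event review to Day 8 or discharge.
2. Record the date of and reason for stopping the dressing.
3. Report adverse events and sacral injuries during wear separately from those after stopping. This serves both the wear-based objective in 3.1 and the period-based endpoint in 5.4.
4. Reconcile 6.5, which sends subjects with events to a bare definition in 18.1, with 18.5, which relies on 8.2 for follow-up that 8.2 does not describe.

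The cost is some wording, fields for the date and reason, and a few extra skin checks by staff already making daily visits. Events after steroid use will be harder to attribute; the separate reporting handles that.

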6.6. Point of enrolment

A subject is considered enrolled in the investigation when the written Informed Consent is obtained. The expected duration for each subject is described in 5.1.

6.7. Subject Identification and Confidentiality

Subjects will be identified on the electronic CRF (e-CRF) and any other document transmitted to the sponsor by the Principal Investigator or clinical site staff, by a unique identification/subject number only.

7. Procedures

7.1. Clinical investigation-related procedures

Screening Visit (V0), Day 0:

- Introduction to the investigation and review of Subject information Form
- Check of in- and exclusion criteria
- Informed Consent Form – ICF signed at Visit 0. If subject wishes to have time for consideration, it is possible and the ICF is signed at Visit 1 the following day
- Inclusion in investigation and allocation of subject number after ICF is signed

Baseline Visit (V1), Day 1:

- Introduction to the investigation and review of Subject information Form
- ICF signed (if not signed at Visit 0)
- Confirmation of inclusion and exclusion criteria if more than 24 hours has passed since Visit 0
- Collect baseline information:
 - Gender (male/female)
 - Age (at time of enrollment (years)
 - Height (cm)
 - Weight (kg)
 - Urinary incontinence (Y/N)
 - Faecal incontinence (Y/N)
 - Date and main reason for admission (e.g., diabetes mellitus, cardiovascular disease, renal disease, pulmonary disease, anaemia, trauma, other)
 - Skin inspection
 - Braden Scale Score
- Apply Biatain Silicone Bandage on the sacral area

Baseline 2-7, skin inspection, Day 2-7:

- Partial lift of test product and skin inspection for signs of non-blanchable erythema over bony prominence/sacral pressure injury over bony prominence

- Re-application of the test product
- Has there been a test product change (Y/N)?
 - if yes, please register what the cause of the change was (dressing soilage, weakened border, damp/saturated dressing, bulky foam, other)

Termination Visit 8, Day 8 or at the day of discharge/earlier termination date:

- Have signs of non-blanchable erythema over bony prominence/sacral pressure injury over bony prominence developed (Y/N)?
 - If yes, please specify stage of pressure injury (*Appendix 3*)
- Was there any non-compliance to the local pressure injury prevention guideline (Y/N)?
 - If yes, explain non-compliance
 - if yes, please include a summary in the comment page

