4.5. Handling of the investigational device

The subjects will be included for up to 7 days.

Subjects that are included in the investigation and applied the investigational product, are expected to wear the product up to 7 days or until discharged. The same product will be applied for the entire test period, however if necessary, due to contamination or rolling edges, the product must be replaced with a new product.

Therefore, the subjects are expected to use approximately 1 product, however the site will be supplied with enough products in case of replacements of products for the duration of the investigation.

In total 67 subjects will be enrolled. To allow for unpredicted dressing changes, 1 patient requires 7 heart shaped/small products, which is per 67 patients: $67 \times 7 = 469$ small sacral products.

Around 30 patients may need the large sacral bandage: $30 \times 7 = 210$ large sacral products.

5. Design of the clinical investigation

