8.2. Risk-benefit for subjects participating in the clinical investigation

The investigation is conducted in accordance with current law and applicable standards, see section 15. Statement of Compliance. The rights, safety and well-being of human subjects shall prevail over the interest of science of society.

Risks in this investigation are considered to be equal to the use of Silicone Sacral bandage products already on the market. Risks associated with the use of sacral bandage products are skin irritation and mechanical trauma. Please also see Adverse events, adverse device effects and device deficiencies section 18.

There is no known interaction between the use of the investigational device and the medication participants can take. Disadvantages of testing (trial engagement) may be the time spent on visits and responding to questions regarding baseline questions.

Possible benefits for the subjects in this investigation, are that subjects might have a lower risk of developing a pressure ulcer during hospitalization, which maybe will be beneficial for the subjects.

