18.6. Reporting and timelines

18.7. Investigator's reporting responsibilities

- PI at each site must assess all (S)AE's that occur at his/her site.

- All serious adverse events and serious adverse device effects must be reported to sponsor within 24 hours of the site becoming aware of the event.
- A device deficiency that could have led to a serious adverse event but did not because suitable action was taken, intervention had been made or because of fortunate circumstances should be reported to sponsor within 24 hours of the site becoming aware of the event.
- New findings and/or updates in relation to already reported serious events should also be reported to sponsor within 24 hours of the site becoming aware of the event.
- Device deficiencies and all adverse device effects related to CE marked Coloplast investigational product and/or comparator must be reported to sponsor within 24 hours of becoming aware of the event.

When reporting the SAE, the relationship to the test material shall be described whether the event is considered

- **Not related**, the event has no temporal relationship with the use of the test material or the procedures.
- **Unlikely related**, the relationship with the use of the test material seems not relevant and/or the event can be reasonably explained by another cause, but additional information may be obtained.
- **Possible related**, the relationship with the use of the test material is weak but cannot be ruled out completely. Alternative causes are also possible (e.g. an underlying or concurrent illness/ clinical condition or/and an effect of another device, drug or treatment). Cases were relatedness cannot be assessed or no information has been obtained should also be classified as possible.
- **Probable related**, the relationship with the use of the test material seems relevant and/or the event cannot reasonably be explained by another cause, but additional information may be obtained.
- **Definitely related/Causal relationship**, the event has a temporal relationship with the test material use/application or procedures.

and the intensity of the event should be considered, as such:

- **Mild**, the intensity of the event is mild with no further action or intervention
- **Moderate**, the intensity of the event will lead to an action or intervention to solve the event

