Remove the remaining protective films, one at a time

Gently run your fingers around the edge of the product to ensure an even and smooth fit to the skin

Intended purpose

The product is intended for moist wound healing and exudate management

Indications

Biatain Silicone

- is indicated for a wide range of low- to highly exuding wounds. This includes acute wounds such as donor sites, post-operative wounds and traumatic wounds, and chronic wounds such as leg ulcers, pressure ulcers and non-infected diabetic foot ulcers
- the product can be used as part of a prophylactic therapy to help prevent skin damage, e.g. pressure injuries, postoperative blistering

Contra-indications

The Biatain Silicone Sacral 15 cm x 19 cm should not be used for patients with a body weight below 10 kg

The Biatain Silicone Sacral 25 cm x 25 cm should not be used for patients with a body weight below 15 kg

Warnings

Re-use of the single use product may create a potential harm to the user. Reprocessing, washing, disinfection and/or sterilisation may compromise product characteristics, causing additional risk of physical harm or infection to the user

Cautions

A health care professional should frequently inspect and manage infected wounds, diabetic wounds and wounds which are solely or partially caused by arterial insufficiency, in accordance with local guidelines

Do not use the product with oxidising solutions e.g. hypochlorite and hydrogen peroxide solutions, as this may cause product degradation. Ensure that any other evaporating solution is completely dried off before applying the product

The use of dressings as part of prophylactic therapy does not preclude the need to continue to develop and follow a comprehensive pressure ulcer prevention protocol, i.e. support surfaces, positioning, nutrition, hydration, skin care, mobility and regular controls

Do not cut the foam part of the product.

Removal

The product should be changed when clinically indicated, when visible signs of exudate approach the edge of the foam or after 7 days.

Loosen the adhesive border before gently lifting the product away from the wound and removing the product.

For prophylactic therapy Biatrin Silicone Sacral and Multishape may be left in place up to 7 days depending on the condition of the skin or as indicated by accepted clinical practice.

Disposal

The product is intended for single use only and should be disposed of in accordance with local guidelines, e.g. with normal household waste.

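### The causality scale has no procedure category, so ADE/SADE classification cannot separate skin effects of the daily study lift from effects of the dressing

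*Combined protocol and SAP*

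**What the plan says.** All references are to the combined protocol and SAP.

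- **Section 7.1** heads the relevant visits "Baseline 2-7, skin inspection, Day 2-7". It requires "Partial lift of test product and skin inspection for signs of non-blanchable erythema" over the bony prominence, and then "Re-application of the test product". If the dressing was changed, the cause is recorded from a short list that includes a weakened border and an open *other* option.
- **Section 4.5** states "The same product will be applied for the entire test period". The exception is that, where necessary "due to contamination or rolling edges, the product must be replaced with a new product".
- **Section 8.2** states "Risks in this investigation are considered to be equal to the use of Silicone Sacral bandage products already on the market", and names skin irritation and mechanical trauma as the risks of such products.
- **Section 18.1** defines an adverse event regardless of cause, and lists the device and the procedures as separate possible causes.
- **Section 18.2** defines an adverse device effect by its relation to use of the device. It lists grades from unlikely upward without defining them.
- **Section 18.3** registers rolling edges as a deficiency only when they exceed what is normal. Normal is not defined.
- **Section 18.7** gives the only defined causality scale, introduced for serious adverse events. Its top grade is met when "the event has a temporal relationship with the test material use/application or procedures".
- **Appendix 1 (instructions for use)** says that in prophylaxis the dressing "may be left in place up to 7 days depending on the condition of the skin or as indicated by accepted clinical practice". It describes application and removal and is silent on re-application.

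**The concern.** Safety is the only primary objective, and section 5.5 says that adverse events and device deficiencies were chosen to examine the safety of this dressing. There is no comparator arm and section 10.4 sets no formal safety criterion. The safety conclusion will therefore rest largely on which events are attributed to the dressing.

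The study itself adds a repeated manipulation of an adhesive product. The two risks named in section 8.2 are ones to which repeated lifting could plausibly contribute. If the forms follow the wording of section 18, a skin effect of the lift and a skin effect of the dressing will carry the same label. Section 10.1 plans no analysis that separates them, so any later separation would depend on free text.

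**Working it through.** **Step 1. Count of lifts.** Inputs: visits 2 to 7 (section 7.1), Table 5 in section 7.2, and 67 enrolled with at least 50 completers (section 10.2).

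- Lifts with re-application per subject: visits 2, 3, 4, 5, 6 and 7 = 6.
- Table 5 also marks a partial lift at visit 8, giving up to 7 lifts. The dressing is removed at that visit, so re-applications stay at 6.
- Ceiling over the study: 67 × 6 = 402. For 50 subjects with full follow-up: 50 × 6 = 300.

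These are maxima. Subjects leave at discharge, the entry criterion asks only for an expected stay of more than 24 hours, and a replaced dressing is itself lifted fewer times.

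**Step 2. The five grades of section 18.7 side by side.**

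| Grade | Names test material | Names procedures | Test applied |
|---|---|---|---|
| Not related | yes | yes | no link in time to either |
| Unlikely | yes | no | link to the material seems irrelevant, and/or another cause reasonably explains the event |
| Possible | yes | no | weak link to the material, not excluded |
| Probable | yes | no | link to the material seems relevant, and/or no other reasonable cause |
| Definitely/causal | yes | yes | link in time to either |

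**Step 3. A test case.** Take a skin injury that appears at a study lift and that the investigator puts down to the lift alone.

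- *Not related* is closed, because the event is linked in time to a procedure.
- *Unlikely* is open, because the lift can be read as another cause that explains the event.
- *Definitely related* is also met, because a link in time to a procedure is enough.

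One event thus satisfies two grades far apart on a scale meant to describe the relationship to the test material. No grade records that it was related to the procedure only.

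**Step 4. Consequence for adverse device effects.** Section 18.2 lists its grades from unlikely upward and defines none of them. Assume that investigators borrow the definitions in section 18.7, the only ones given. The event in step 3 then falls within the listed device-effect grades whichever of the two is chosen. The footnote to Table 6 exempts temporary redness on removal of the dressing. It does not mention partial lifts, and redness of abnormal intensity or duration still counts.

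**Step 5. Consequence for the endpoints.** The primary endpoint counts all adverse events, and section 18.1 includes them whatever their cause. A change of grade moves no event in or out of that count. What changes is the split into device effects and other events.

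**Step 6. Device deficiencies, a separate gap.** Section 18.3 has no causality step, so the wording in section 18.7 plays no part here. The gap is that the normal extent of rolling edges is undefined, so it is unclear whether it refers to an undisturbed dressing or to one lifted daily. Neither section 18.3 nor the list of change reasons in section 7.1 has an option identifying border failure that follows a study lift.

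**The case against.** The case against is substantial, and it limits the point.

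- **Harm from peeling an adhesive may properly be a device effect.** Section 18.2 includes events from operation of the device and from use error. This stands as a possible judgement for an individual event. It argues for recording both relationships, not for having no procedure grade.
- **The scale is introduced for serious events, and three of its five grades name only the test material.** Both are true. But the end grades decide what is excluded and what is causal, and no other defined scale is offered for non-serious events.
- **Daily checking may be ordinary care.** The instructions tie wear time to skin condition and clinical practice, and their cautions call for regular controls. A reader might infer that section 7.1 contradicts the instructions. The documents do not support that: the instructions are silent on re-application and do not forbid it. They also do not say whether daily lifting is routine, so the equal-risk statement in section 8.2 is unexplained rather than shown to be wrong.
- **Misattribution would count against the dressing, and there is no pass/fail rule for safety.** This stands and is why the point is minor. It does not make the attribution informative.
- **Events are reviewed at each visit from baseline on, and AE/ADE/DD records are fully monitored.** This secures timely and complete records. It does not create a category that the scale lacks.

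A reader might also infer that every weakened border becomes a device deficiency, or that the deficiency form lacks a cause field. The first conflicts with the filter in section 18.3. The second cannot be checked, because the forms are not reproduced, and section 7.1 does ask for the cause of a dressing change.

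**Conclusion.** The point holds as a minor one. As written, section 18.7 does not allow an event due only to the study lift to be graded as unrelated to the test material, and it allows the highest grade. ADE/SADE classification and the interpretation of the safety result therefore mix two causes that section 18.1 treats as distinct. For non-serious events this rests on the assumption in step 4. The deficiency records have a parallel but independent gap.

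The size of any misattribution is unknown. The figure of 402 is a ceiling on re-applications if all 67 subjects stay the full period, and it says nothing about how many events follow. If a share p of device-attributed events were due to the lift alone, the device count would be overstated by a factor of 1/(1 − p): 1 at p = 0, 2 at p = 0.5, and without bound as p approaches 1. A reader might infer a doubling, but that needs p = 0.5, and the documents give no value for p.

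A reader might also infer that the primary endpoint is biased. It is not, because it counts adverse events of every cause.

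**What to change.** 1. In sections 18.2 and 18.7 and on the adverse event and serious adverse event forms, grade two relationships separately: to the dressing, and to the study procedure (partial lift and re-application). Word all five grades on the same basis, and state that the definitions also apply to non-serious events.
2. On the device deficiency and dressing-change records, add an option showing that the failure followed a study lift.
3. In section 10.1, plan to report adverse device effects and deficiencies with and without those attributed only to the procedure.
4. Reconcile the equal-risk statement in section 8.2 with the procedure in section 7.1.

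No change to the inspection schedule or to care is proposed. The cost is one extra field per form, one table split, and a second causality judgement by the investigator for each event.
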